- ⁵ Liver biopsies will be obtained in subjects <18 years of age. An historical liver biopsy obtained within 26 weeks prior to Screening and adequate for histological examination may be used in lieu of a Screening biopsy. The liver biopsy should be obtained via the transjugular method in those subjects with advanced liver disease, where local regulations and facilities permit, so the hepatic venous pressure gradient can be measured and collected during this procedure. Any biopsy done for other medical reasons during the course of the study will also be evaluated by central pathologists (stained and unstained samples). Subjects who have any prior liver biopsy unstained sections will be analyzed in the same method, if available. Liver biopsy at Week 48 can be ± 2 weeks, for scheduling considerations.
- ⁶ A historical endoscopic biopsy result will be accepted in lieu of a Screening biopsy if performed within 1 year of Screening. A follow-up biopsy will be performed only at Week 24, if evidence of substrate accumulation was present at Screening. Week 24 biopsy is optional for pediatric subjects. However, any biopsy performed during the study will be recorded in the CRF.

- ⁷ Transient elastography will be performed in locales where technology is available.
- ⁸ Denver II assessments will be completed for subjects who are ≤6 years old during the screening period.
- ⁹ Age-appropriate health-related quality of life questionnaires will be completed prior to any other study procedures.
- ¹⁰ Refer to [Section 5.9](#) for a list of analytes in each laboratory panel. Subjects will refrain from ingestion of alcohol for 24 hours prior to the collection of blood samples for lipid and liver panels. Labs will be drawn as blood volume and clinical status allow. See laboratory manual or SOM for details. Prior to any dose change, serum lipid, serum liver, hematology, chemistry, ferritin and hs-CRP shall be obtained; ADA and PK assessments will be obtained on the day of any study drug dose change, as described in [Section 5.9.4](#). Serum lipid and serum liver assessments should be taken 4, 8, and 12 Weeks following any study-drug or lipid drug dose change.
- ¹¹ A sample will be obtained at Screening, or as soon as practically possible thereafter ([Section 5.9.3](#))
- ¹² For female subjects of childbearing potential only. Serum pregnancy test is required at screening. Urine pregnancy tests at all designated visits thereafter.
- ¹³ PK Samples will be taken at Baseline, Week 24, Week 48, and on the first day of any dose modification as per the table in [Section 5.9.4](#), as blood volume allows.
- ¹⁴ Vital signs will be measured at one time point during Screening. On the day of study drug dosing, vitals will be collected pre-dose, every 30 minutes (±10 min) during the infusion, and every 30 minutes (±10 min) from 0 to 2 hours after infusion. Beginning at Week 24, the post-infusion period for vital sign monitoring may be shortened from 2 hours to 1 hour for subjects who have completed at least 22 weeks of treatment with no occurrence of moderate or severe IARs, contingent upon approval from the Sponsor.
- ¹⁵ Please refer to the IMP manual for detailed instructions on duration and rate of infusions. After Week 24, infusion time may be decreased to 1 hour. If the infusion is not well tolerated; the infusion rate may be decreased ([Section 6.5.2](#)). If dose is increased to weekly infusion, the allowable window for treatment is ±2 days, and infusions must be at least 5 days apart.
- ¹⁶ Subjects/parents should also be queried about any changes in lipid-lowering medications or lipid-lowering diets, UDCA, metformin, glitazones, or vitamin E.

Schedule II - Assessments for Pediatric Subjects (Subjects <18 years) - Week 52 to Week 96 of Treatment Period

| Assessments* | Treatment | | | | | | | | | | | |
|---|------------------------------|----------------|----------------|----------------|----------------|----------------|----------------|----------------|----------------|----------------|----------------|----------------|
| | Week 52 | Week 56 | Week 60 | Week 64 | Week 68 | Week 72 | Week 76 | Week 80 | Week 84 | Week 88 | Week 92 | Week 96 |
| | ±7 days | ±7 days | ±7 days | ±7 days | ±7 days | ±7 days | ±7 days | ±7 days | ±7 days | ±7 days | ±7 days | ±7 days |
| 12-lead ECG | | | | | | | | | | | | X ^p |
| Physical Examination ¹ | | | X ^p | | | X ^p | | | X ^p | | | X ^p |
| Height (<2 years) ² | Every two weeks ^p | | | | | | | | | | | |
| Weight (<2 years) ² | Every two weeks ^p | | | | | | | | | | | |
| Height (2-18 years) | | | X ^p | | | X ^p | | | X ^p | | | X ^p |
| Weight (2-18 years) | Every two weeks ^p | | | | | | | | | | | |
| Abdominal MRI ³ | | | | | | | | | | | | X ^p |
| Carotid MRI | | | | | | | | | | | | X ^p |
| Liver Biopsy ⁴ | | | | | | | | | | | | X ^p |
| Hepatic Venous Pressure Gradient | | | | | | | | | | | | X ^p |
| Endoscopic Biopsy ⁵ | | | | | | | | | | | | X ^p |
| Transient elastography ⁶ | | | | | | | | | | | | X ^p |
| Denver II ⁷ | | | | | | X ^p | | | | | | X ^p |
| HRQOL (subjects ≥5 years) ⁸ | | | | | | X ^p | | | | | | X ^p |
| Clinical Laboratory Tests⁹ | | | | | | | | | | | | |
| LAL Enzyme Activity (DBS) | | | | | | | | | | | | |
| Liver Panel | | | X ^p | | | X ^p | | | X ^p | | | X ^p |
| Lipid Panel | | | X ^p | | | X ^p | | | X ^p | | | X ^p |
| Hematology, Electrolytes, Glucose, Creatinine | | | X ^p | | | X ^p | | | X ^p | | | X ^p |
| Coagulation Panel | | | X ^p | | | X ^p | | | X ^p | | | X ^p |
| Pregnancy Test ¹⁰ | X ^p | X ^p | X ^p | X ^p | X ^p | X ^p | X ^p | X ^p | X ^p | X ^p | X ^p | X ^p |
| Anti-drug Antibody | | | X ^p | | | X ^p | | | X ^p | | | X ^p |
| Urinalysis | | | X ^p | | | X ^p | | | X ^p | | | X ^p |
| Macrophage Activation Markers | | | X ^p | | | X ^p | | | X ^p | | | X ^p |
| HbA1c | | | X ^p | | | X ^p | | | X ^p | | | X ^p |
| Blood Exploratory Biomarkers | | | X ^p | | | X ^p | | | X ^p | | | X ^p |
| Vital Signs ¹¹ | Every two weeks ^p | | | | | | | | | | | |
| Sebelipase alfa Infusion ¹² | Every two weeks | | | | | | | | | | | |
| Adverse Event Assessment | Continuous | | | | | | | | | | | |
| Concomitant Meds/Treatment ¹³ | Continuous | | | | | | | | | | | |

* Note: All study visits will be scheduled relative to Day 0 (Baseline); consecutive infusions must be administered at least 7 days apart. Assessments performed for subjects of a certain age are based on the subject's age on the date that informed consent is obtained.

^P Pre-infusion

- ¹ All physical examinations will include assessment of liver and spleen size, lymphadenopathy, arterial disease, and skin manifestations of hepatic disease or dyslipidemia. Physical exam findings should drive any additional functional assessments.
- ² For subjects <2 years of age, weight, recumbent length or height, and abdominal circumference will be measured at all visits; mid-upper arm circumference will be measured. Head circumference will be measured in children up to 3 years of age.
- ³ Abdominal MRI should be considered in subjects receiving general anesthesia and/or sedation for other procedures at the indicated time points. There should be at least 3 months between each MRI. Ultrasound may be substituted at a given time point if an MRI is contraindicated.
- ⁴ Liver biopsies will be obtained in subjects <18 years of age. The liver biopsy should be obtained via the transjugular method in those subjects with advanced liver disease, where local regulations and facilities permit, so the hepatic venous pressure gradient can be measured and collected during the procedure. Any biopsy done for other medical reasons during the course of the study will also be evaluated by central pathologists (stained and unstained samples). Subjects who have any prior liver biopsy unstained sections will be analyzed in the same method, if available. A liver biopsy at Week 96 is optional.
- ⁵ Any endoscopic biopsy performed during the study will be recorded in the CRF.
- ⁶ Transient elastography will be performed in locales where technology is available.
- ⁷ Denver II assessments will be completed for subjects who are ≤6 years old during the screening period at the time of Informed Consent.
- ⁸ Age-appropriate health-related quality of life questionnaires will be completed prior to any other study procedures.
- ⁹ Refer to [Table 1](#) for a list of analytes in each laboratory panel. Subjects will refrain from ingestion of alcohol for 24 hours prior to collection of blood samples for lipid and liver panels. Labs will be drawn as blood volume and clinical status allow. See laboratory manual or SOM for details. Prior to any dose change, serum lipid, serum liver, hematology, chemistry, ferritin and hs-CRP shall be obtained; ADA and PK assessments will be obtained on the day of any study drug dose change, as described in [Section 5.9.4](#). Serum lipid and serum liver assessments should be taken 4, 8, and 12 Weeks following any study-drug or lipid drug dose change.
- ¹⁰ For female subjects of childbearing potential only. Serum pregnancy test is required at Screening. Urine pregnancy tests at all designated visits thereafter.
- ¹¹ On the day of study drug dosing, vitals will be collected pre-dose, every 30 minutes (±10 min) during the infusion, and every 30 minutes (±10 min) from 0 to 2 hours after infusion. Beginning at Week 24, the post infusion period for vital sign monitoring may be shortened from 2 hours to 1 hour for subjects who have completed at least 22 weeks of treatment with no occurrence of moderate or severe IARs, contingent upon approval from the Sponsor.
- ¹² Please refer to IMP manual for detailed instructions on duration and rate of infusions. After Week 24, infusion time may be decreased to 1 hour. If the infusion is not well tolerated; the infusion rate may be decreased ([Section 6.5.2](#)). If dose is increased to weekly infusion, the allowable window for treatment is ±2 days, and infusions must be at least 5 days apart.
- ¹³ Subjects/parents should also be queried about any changes in lipid-lowering medications or lipid-lowering diets, UDCA, metformin, glitazones, or vitamin E.

Schedule II - Assessments for Pediatric Subjects (Subjects <18 years) - Expanded Treatment Period through Follow-up

| Assessments* | Expanded Treatment | | | | | | | | | | | | End of Study Visit (Early Withdrawal) | Follow-up Call 4 Weeks (+7) days after last infusion |
|---|------------------------------|----------------|----------------|----------------|----------------|----------------|----------------|----------------|----------------|----------------|----------------|----------------|---------------------------------------|--|
| | Week 100 | Week 104 | Week 108 | Week 112 | Week 116 | Week 120 | Week 124 | Week 128 | Week 132 | Week 136 | Week 140 | Week 144 | | |
| | ±7 days | ±7 days | ±7 days | ±7 days | ±7 days | ±7 days | ±7 days | ±7 days | ±7 days | ±7 days | ±7 days | ±7 days | | |
| 12-lead ECG | | | | | | | | | | | | X ^p | X | |
| Physical Examination ¹ | | | X ^p | | | X ^p | | | X ^p | | | X ^p | X | |
| Height (<2 years) ² | Every two weeks ^p | | | | | | | | | | | | X | |
| Weight (<2 years) ² | Every two weeks ^p | | | | | | | | | | | | X | |
| Height (2-18 years) | | | X ^p | | | X ^p | | | X ^p | | | X ^p | X | |
| Weight (2-18 years) | Every two weeks ^p | | | | | | | | | | | | X | |
| Abdominal MRI ³ | | | | | | | | | | | | X ^p | X | |
| Carotid MRI | | | | | | | | | | | | X ^p | X | |
| Liver Biopsy ⁴ | | | | | | | | | | | | | X | |
| Hepatic Venous Pressure Gradient | | | | | | | | | | | | X ^p | | |
| Endoscopic Biopsy ⁵ | | | | | | | | | | | | | | |
| Transient elastography ⁶ | | | | | | | | | | | | X ^p | X | |
| Denver II ⁷ | | | | | | X ^p | | | | | | X ^p | X | |
| HRQOL (subjects ≥5 years) ⁸ | | | | | | X ^p | | | | | | X ^p | X | |
| Clinical Laboratory Tests⁹ | | | | | | | | | | | | | | |
| LAL Enzyme Activity (DBS) | | | | | | | | | | | | | X | |
| Liver Panel | | | X ^p | | | X ^p | | | X ^p | | | X ^p | X | |
| Lipid Panel | | | X ^p | | | X ^p | | | X ^p | | | X ^p | X | |
| Hematology, Electrolytes, Glucose, Creatinine | | | X ^p | | | X ^p | | | X ^p | | | X ^p | X | |
| Coagulation Panel | | | X ^p | | | X ^p | | | X ^p | | | X ^p | | |
| Pregnancy Test ¹⁰ | X ^p | X ^p | X ^p | X ^p | X ^p | X ^p | X ^p | X ^p | X ^p | X ^p | X ^p | X ^p | X | |
| Anti-drug Antibody | | | X ^p | | | X ^p | | | X ^p | | | X ^p | X | |
| Urinalysis | | | X ^p | | | X ^p | | | X ^p | | | X ^p | X | |
| Macrophage Activation Markers | | | X ^p | | | X ^p | | | X ^p | | | X ^p | X | |
| HbA1c | | | X ^p | | | X ^p | | | X ^p | | | X ^p | X | |
| Blood Exploratory Biomarkers | | | X ^p | | | X ^p | | | X ^p | | | X ^p | X | |
| Vital Signs ¹¹ | Every two weeks ^p | | | | | | | | | | | | X | |
| Sebelipase alfa Infusion ¹² | Every two weeks | | | | | | | | | | | | | |
| Adverse Event Assessment | Continuous | | | | | | | | | | | | | |
| Concomitant Meds/Treatment ¹³ | Continuous | | | | | | | | | | | | | |

* Note: All study visits will be scheduled relative to Day 0 (Baseline); consecutive infusions must be administered at least 7 days apart. Assessments performed for subjects of a certain age are based on the subject's age on the date that informed consent is obtained.

^P Pre-infusion

- ¹ All physical examinations will include assessment of liver and spleen size, lymphadenopathy, arterial disease, and skin manifestations of hepatic disease or dyslipidemia. Physical exam findings should drive any additional functional assessments.
- ² For subjects <2 years of age, weight, recumbent length or height, and abdominal circumference will be measured at all visits; mid-upper arm circumference will be measured. Head circumference will be measured in children up to 3 years of age.
- ³ Abdominal MRI should be considered in subjects receiving general anesthesia and/or sedation for other procedures at the indicated time points. There should be at least 3 months between each MRI. Ultrasound may be substituted at a given time point if an MRI is contraindicated.
- ⁴ Liver biopsies will be obtained in subjects <18 years of age. The liver biopsy should be obtained via the transjugular method in those subjects with advanced liver disease, where local regulations and facilities permit, so the hepatic venous pressure gradient can be measured and collected during the procedure. Any biopsy done for other medical reasons during the course of the study will also be evaluated by central pathologists (stained and unstained samples). Subjects who have any prior liver biopsy unstained sections will be analyzed in the same method, if available.
- ⁵ Any endoscopic biopsy performed during the study will be recorded in the CRF.
- ⁶ Transient elastography will be performed in locales where technology is available.
- ⁷ Denver II assessments will be completed for subjects who are ≤6 years old during the screening period at the time of Informed Consent.
- ⁸ Age-appropriate health-related quality of life questionnaires will be completed prior to any other study procedures.
- ⁹ Refer to [Table 1](#) for a list of analytes in each laboratory panel. Subjects will refrain from ingestion of alcohol for 24 hours prior to collection of blood samples for lipid and liver panels. Labs will be drawn as blood volume and clinical status allow. See laboratory manual or SOM for details. Prior to any dose change, serum lipid, serum liver, hematology, chemistry, ferritin and hs-CRP shall be obtained; *ADA and PK assessments will be obtained on the day of any study drug dose change, as described in Section 5.9.4.* Serum lipid and serum liver assessments should be taken 4, 8, and 12 Weeks following any study-drug or lipid drug dose change.
- ¹⁰ For female subjects of childbearing potential only. Serum pregnancy test is required at Screening. Urine pregnancy tests at all designated visits thereafter.
- ¹¹ On the day of study drug dosing, vitals will be collected pre-dose, every 30 minutes (±10 min) during the infusion, and every 30 minutes (±10 min) from 0 to 2 hours after infusion. Beginning at Week 24, the post infusion period for vital sign monitoring may be shortened from 2 hours to 1 hour for subjects who have completed at least 22 weeks of treatment with no occurrence of moderate or severe IARs, contingent upon approval from the Sponsor.
- ¹² Please refer to IMP manual for detailed instructions on duration and rate of infusions. After Week 24, infusion time may be decreased to 1 hour. If the infusion is not well tolerated; the infusion rate may be decreased ([Section 6.5.2](#)). If dose is increased to weekly infusion, the allowable window for treatment is ±2 days, and infusions must be at least 5 days apart.
- ¹³ Subjects/parents should also be queried about any changes in lipid-lowering medications or lipid-lowering diets, UDCA, metformin, glitazones, or vitamin E.

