4.6.2. Procedures for Discontinuation

If a subject is discontinued from the study, the subject or their parent or legal guardian will be asked about the presence of AEs. The date and reason(s) for discontinuation will be recorded in the eCRF. The date of discontinuation will be the date that the Investigator discontinues the subject from the study or that the subject notifies the Investigator of the decision to discontinue. The reason for discontinuation will be that identified by the Investigator or voluntarily reported by the subject. If a subject withdraws consent and does not voluntarily provide a reason for discontinuation, "withdrawal of consent" will be recorded in the eCRF.

A subject will be considered discontinued due to an AE if the subject received any infusion or partial infusion of study drug, but did not complete the study because of an AE, whether or not the AE is considered drug related.

Subjects who prematurely discontinue treatment in the study will have an end-of-study visit prior to withdrawal, and a follow-up call at least 4 weeks after the last infusion, whenever feasible (see [Appendix B](#) for a list of the assessments to be performed at this visit). Post-study SAEs

and IARs will be reported according to [Section 7.4](#) for all subjects prematurely discontinuing treatment in the study.

When a subject fails to return for scheduled assessments, efforts must be made to contact the subject (or the subject's parent or legal guardian) to determine a reason for the failure to return. If 2 or more consecutive visits are missed, the Investigator should contact the Sponsor to determine whether the subject will be allowed to continue on study. After all reasonable efforts to reach a subject (or the subject's parent or legal guardian) have been exhausted, the subject will be identified as lost to follow up in the eCRF.

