5.5. Physical Examination

A complete, age-appropriate physical examination will be performed by the Investigator or qualified designee, at the time points specified in [Appendix B](#). The examination will include an assessment of the subject's general appearance, skin, head (including head circumference for children up to 3 years of age), eyes, ears, nose, throat, heart, lungs, abdomen, extremities/joints, and neurological status. Whenever possible, the same person should perform the physical examination at each study visit. Abnormal findings will be recorded in the eCRF.

Every physical examination will also include the following:

- Child-Pugh Score (see [Appendix A](#));
- Abdominal photograph for subjects < 4 years of age at Screening;
- Liver size: A clinical assessment of liver size (palpable/non palpable and centimeters below costal margin), regularity (smooth/nodular), and sensitivity (tender/nontender);
- Spleen size: A clinical assessment of spleen size (palpable/nonpalpable and centimeters below costal margin), regularity (smooth/nodular), and sensitivity (tender/nontender);
- Lymphadenopathy: An assessment of the size, location, and character of any palpable lymph nodes. Areas to be examined include cephalic (occipital, preauricular, postauricular, submental, submandibular), cervical, clavicular, axillary, and inguinal. Any enlarged nodes will be characterized as tender or nontender;
- Arterial disease: A clinical assessment of the right and left posterior tibialis and dorsalis pedis pulses and carotid bruits;
- Skin manifestations: A clinical assessment of signs of liver disease and portosystemic anastomoses such as periumbilical venous engorgement (caput medusae), spider nevia, or gynecomastia, dylipidemia such as xanthomas (tendinous, tuberos) and xanthelasma, and allergies including assessment of allergic skin rashes.

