Appendix A: Child-Pugh Score and Classification

The Child-Pugh score is calculated as the sum of the individual scores for each of the following 5 factors:

| Parameter | | Score | | |
|---------------------------------------|-------------------|---------|-------------------|-------------------|
| | | 1 Point | 2 Points | 3 Points |
| Total Serum Bilirubin | mg/dL | <2.0 | 2.0 to 3.0 | >3.0 |
| | µmol/L | <34 | 34 to 51 | >51 |
| Serum Albumin | g/dL | >3.5 | 3.0 to 3.5 | <3.0 |
| | g/L | >35 | 30 to 35 | <30 |
| Prothrombin Time | Seconds prolonged | 0 to 4 | 4 to 6 | >6 |
| | INR | <1.7 | 1.7 to 2.3 | >2.3 |
| Ascites | | None | Easily controlled | Poorly controlled |
| Hepatic Encephalopathy | | None | Minimal | Advanced |
| INR = International Normalized Ratio | | | | |
| Source: Harrison's Manual of Medicine | | | | |

The Child-Pugh classification is then determined as follows:

| Child-Pugh Classification | Total Child-Pugh Score |
|---------------------------|------------------------|
| Class A | 5 to 6 |
| Class B | 7 to 9 |
| Class C | 10 to 15 |

Appendix B: Schedules of Assessments**Schedule I - Assessments for Adult Subjects (Subjects ≥18 years) - Screening to Week 48 of Treatment Period**

| Assessments* | Screening | Treatment | | | | | | | | | | | | | |
|---|------------------|----------------|------------------------------|----------------|----------------|----------------|----------------|----------------|----------------|----------------|----------------|----------------|----------------|----------------|----------------|
| | Day -45 to Day 0 | Day 0 | Week 2 | Week 4 | Week 8 | Week 12 | Week 16 | Week 20 | Week 24 | Week 28 | Week 32 | Week 36 | Week 40 | Week 44 | Week 48 |
| | | | ±7 days | ±7 days | ±7 days | ±7 days | ±7 days | ±7 days | ±7 days | ±7 days | ±7 days | ±7 days | ±7 days | ±7 days | ±7 days |
| Informed Consent/Assent | X | | | | | | | | | | | | | | |
| Inclusion/Exclusion Criteria | X | X ^p | | | | | | | | | | | | | |
| Medical History | X | | | | | | | | | | | | | | |
| AUDIT | X | | | | | | | | | | | | | | |
| Historical DNA Results ¹ | X | | | | | | | | | | | | | | |
| 12-lead ECG | X | | | | | | | | | | | | | | X ^p |
| Physical Examination ² | X | X ^p | | | | X ^p | | | X ^p | | | X ^p | | | X ^p |
| Height | | X ^p | | | | | | | | | | | | | |
| Weight | | X ^p | Every two weeks ^p | | | | | | | | | | | | |
| Abdominal MRI ³ | X | | | | | | | | | | | | | | X ^p |

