7.3.1. Handling of Dropouts or Missing Data

All data will be analyzed as they were collected in the database. Missing data in general will not be imputed, limited imputation techniques if applied are described in Section 9.

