9.4.6 United Kingdom Model for End-Stage Liver Disease

The UK-MELD is calculated as (5.395 x lnINR) + (1.485 x ln serum creatinine) + (3.13 x ln serum bilirubin) - (81.565 x ln serum sodium) + 435.

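### The pediatric early-withdrawal visit omits the coagulation panel, so Child-Pugh and UK-ELD have no scheduled INR at that visit

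*Protocol*

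**What the plan says.** Protocol Section 4.6.2 gives subjects who stop treatment early an end-of-study visit and refers to Appendix B "for a list of the assessments to be performed at this visit". The only list there is the end-of-study (early withdrawal) column in the last part of each schedule, so it governs withdrawals at any point in the study.

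In the pediatric schedule (Schedule II) that column is blank in the "Coagulation Panel" row. In the adult schedule (Schedule I) the same row is marked. The pediatric column does mark the physical examination, the liver panel and the row "Hematology, Electrolytes, Glucose, Creatinine".

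Protocol Section 5.5 says "Every physical examination will also include the following", and the Child-Pugh score heads the list that follows. Appendix A states "The Child-Pugh score is calculated as the sum of the individual scores for each of the following 5 factors"; prothrombin time, in seconds prolonged or as INR, is one of the five. SAP Section 9.4.6 opens its formula with "The UK-MELD is calculated as (5.395 x lnINR" and adds terms in creatinine, bilirubin and sodium. In Protocol Table 1, PT (INR) appears only under the coagulation parameters.

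On gaps in the data, SAP Section 7.3.1 says "Missing data in general will not be imputed", and the limited rules in SAP Section 9 do not include carrying an INR forward.

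**The concern.** The protocol asks for a Child-Pugh score at the pediatric withdrawal visit and leaves out one of its five inputs. The same omission removes one of the four inputs of UK-ELD. Both scores are listed efficacy endpoints (Protocol Section 3.2.1.2, SAP Section 5.2.1), and coagulation parameters also belong to the safety laboratory summaries in SAP Section 7.2.3. At stake are the exit value of two secondary endpoints and the exit coagulation result, in children who leave early.

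The blank looks like an oversight. It is the only laboratory row left empty in the pediatric column. Sparing blood does not explain it: coagulation is a Tier 1 test (Section 5.9.1), while Tier 2 tests such as macrophage activation markers and exploratory biomarkers (Section 5.9.2) are marked at the same visit.

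**Working it through.** There is no stated figure to reproduce; the check is of the schedule and of what a missing INR leaves open.

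**1. Is the blank a column shift?** The expanded-period table has 12 week columns plus end of study plus follow-up, which is 14 data cells. Each row checked has 14 cells.

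| Row, end-of-study (early withdrawal) column | Pediatric | Adult |
|---|---|---|
| Physical examination | marked | marked |
| Liver panel | marked | marked |
| Hematology, electrolytes, creatinine | marked | marked |
| Coagulation | **blank** | marked |
| Urinalysis | marked | marked |

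So a shift of columns is ruled out.

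**2. Which inputs are scheduled at that visit?**

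- Child-Pugh: bilirubin and albumin (liver panel), ascites and encephalopathy (clinical) are available; prothrombin time is not. That is 4 of 5 factors.
- UK-ELD: creatinine and sodium (chemistry) and bilirubin (liver panel) are available; INR is not. That is 3 of 4 inputs.

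**3. What does the missing Child-Pugh factor leave open?** It scores 1 to 3 points. Let S be the sum of the other four factors (4 to 12). The total lies between S + 1 and S + 3. Classes are A = 5–6, B = 7–9, C = 10–15.

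| S | Possible totals | Possible class |
|---|---|---|
| 4 | 5, 6, 7 | A or B |
| 5 | 6, 7, 8 | A or B |
| 6 | 7, 8, 9 | B |
| 7 | 8, 9, 10 | B or C |
| 8 | 9, 10, 11 | B or C |
| 9 to 12 | 10 to 15 | C |

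The total is undetermined in every case. The class is undetermined when S is 4, 5, 7 or 8.

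**4. What does the missing INR leave open in UK-ELD?** The missing term is 5.395 × ln(INR). The documents give no INR distribution, so the upper limits here are assumptions, with 1.0 as the lower limit:

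- up to 1.7: 5.395 × ln 1.7 = 2.86 points
- up to 2.3: 5.395 × ln 2.3 = 4.49 points
- up to 3.0: 5.395 × ln 3.0 = 5.93 points

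**5. How old can the last scheduled INR be?** Pediatric coagulation is drawn at Screening (Day −45 to Day 0), at Week 12, and every 12 weeks after that.

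- After Week 12: nearly 12 weeks between scheduled draws. With the ±7-day window at both ends, (84 + 14)/7 = 14 weeks.
- Leaving just before Week 12: the only scheduled value is from Screening, so up to about (45 + 84)/7 = 18.4 weeks before visit windows. Such a child has no scheduled post-baseline INR, and so no post-baseline value of either score from scheduled tests.

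**6. After the change.** With the coagulation panel marked, every laboratory input of both scores is scheduled at the visit.

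**The case against.** Four points can be made on the other side.

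*The scores need not be lost.* A reader might infer that every child who withdraws loses both scores. The documents do not support that. The withdrawal visit may coincide with a 12-weekly coagulation visit, and Section 5 allows symptom-directed unscheduled assessments. Nothing in Section 5.5, Appendix A or SAP Section 9.4.6 says the INR must come from the same day. On Day 0 both schedules already call for a physical examination, and hence Child-Pugh, with coagulation drawn only at Screening. This stands as a limit on the claim. It does not remove the gap: none of these sources is required at withdrawal, and neither document says whether, or how far back, an earlier INR may be used.

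*Bias.* A reader might also infer that the omission tilts the results towards stable children. That is not shown. SAP Section 7 summarizes visits as collected, so later scheduled weeks lose a withdrawn child with or without an exit INR. Reasons for leaving are not only clinical: under Section 4.6.1, subjects in the expanded period stop once the drug is registered and available in their region. This objection stands in full.

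*Reading of the table.* Counting cells rules out a shifted column but not a single mark lost when the page was converted to text. A look at the original page settles it.

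*Importance.* The analyses are descriptive, the primary objective is safety, and the listed Child-Pugh endpoint concerns subjects in class B or C at Baseline. That supports a low rating, although SAP Section 7.2.4 also summarizes Child-Pugh for the whole Full Analysis Set.

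**Conclusion.** The point holds as a minor schedule inconsistency. The pediatric early-withdrawal column conflicts with Section 5.5 and differs from the adult schedule without a stated reason. Unless an INR happens to be available from a coinciding or unscheduled test, the visit as scheduled gives neither a Child-Pugh total nor a UK-ELD score, and no exit coagulation value.

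The number of children affected cannot be derived: about 30 subjects of all ages are planned, and the documents give neither the pediatric share nor a dropout rate. No error rate or power is involved. The conclusion rests on the blank cell being as printed and on Appendix B being the full list for that visit, as Section 4.6.2 implies.

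**What to change.** Mark the coagulation panel at the end-of-study (early withdrawal) visit in Schedule II, so that it agrees with Schedule I and Section 5.5. The cost is one local PT/INR at a visit where blood is already drawn, and a small extra volume that stays subject to the blood-volume limits in Section 5.9. This is a cheap improvement.

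Where those limits prevent the draw, or for children who have already left, the SAP should state whether an earlier INR may be used and how old it may be, or that the scores are left missing.
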